3.4 Safety Endpoint(s)

Safety evaluations include adverse event (AE) monitoring, physical examinations, vital sign measurements, electrocardiograms (ECGs), and clinical laboratory testing (hematology, chemistry, and urinalysis) as measures of safety and tolerability for the entire study duration.

An independent external Cardiovascular Adjudication Committee (CAC) will adjudicate all blinded cardiovascular and cerebrovascular events, embolic/thrombotic events and deaths, as defined in the CAC charter.

4.0 Analysis Populations

The Full Analysis Set (FAS) includes all randomized subjects who have received at least 1 dose of study drug. Subjects will be grouped according to treatment as randomized. The FAS will be used for all efficacy analyses and summary of baseline characteristics.

The Safety Analysis Set consists of all subjects who have received at least 1 dose of study drug. For the Safety Analysis Set, subjects are assigned to a treatment group based on the treatment actually received, regardless of the treatment randomized.

5.0 Subject Disposition

The total number of subjects who were screened, enrolled (randomized), and treated will be summarized.

A summary of subject accountability will be provided where the number of subjects in each of the following categories will be summarized for each treatment group:

- Subjects enrolled (randomized) in the study.
- Subjects who took at least one dose of study drug.
- Subjects who completed study drug up to Week 24.
- Subjects who completed study drug up to Week 48.
- Subjects who prematurely discontinued study drug (all reasons and primary reason).
- Subjects who completed Week 24 visits.
- Subjects who completed the study.
- Number of subjects who elect to participate in the long-term extension Study M20-186.

For end of study participation, the number and percentage of subjects who completed the protocol-defined follow-up period (or did not with associated reasons) will be summarized overall and by treatment group.

6.0 Study Drug Duration and Compliance

6.1 Study Drug Duration

The duration of exposure to study drug will be summarized by each treatment group using the Safety Analysis Set population.

- Duration of exposure = the last study drug dose date – the first study drug dose date + 1.

For the Safety Analysis Set, duration of treatment will be summarized for each treatment group and for all investigational study drug dose groups combined. The duration of treatment is defined for each subject as last dose date minus first dose date + 1. Duration of treatment will be summarized using the number of subjects, mean, standard deviation, minimum, median and maximum for duration of Study M19-130. In addition, the number and percentage of subjects exposed to study drug will be summarized for the following exclusive duration intervals:

- ≥ 1 day
- ≥ 29 days
- ≥ 57 days
- ≥ 85 days
- ≥ 113 days
- ≥ 141 days
- ≥ 169 days
- ≥ 197 days
- ≥ 225 days
- ≥ 253 days
- ≥ 281 days
- ≥ 309 days
- ≥ 337 days

6.2 Study Drug Compliance

Study drug compliance will be summarized for each treatment group for SA population. Descriptive statistics will be provided including sample size, mean, standard deviation, median, minimum, and maximum.

Treatment compliance (TC) will be calculated using the following formula for tablets and capsules respectively:

$$TC = \frac{\text{Total number of tablets/capsules taken}}{(\text{last dose date} - \text{first dose date} + 1) \times \langle \text{number of tablets/capsules per day} \rangle} \times 100\%$$

- The total number of tablets/capsules taken will be calculated as the total number of tablets/capsules dispensed minus the total number of tablets/capsules returned.

Note: If the bottle is not returned, total number of tablets/capsules returned is assumed to be 0.

- In M19-130: number of tablets per day is 1 and number of capsules per day is 3.

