5.7 Study Drug

Elsubrutinib, upadacitinib, or matching placebo manufactured by AbbVie (Table 2) will be administered on Day 1 (Baseline) and should be taken at approximately the same time each day. Subjects will be instructed to take study drugs orally, which includes only 1 capsule of elsubrutinib or placebo from each of the 3 dispensed bottles per day, with or without food, and only 1 tablet of upadacitinib or placebo from the dispensed bottle per day, with or without food. Subjects will be instructed to take only 1 capsule or tablet from each dispensed bottle per day. If subjects should forget to take their elsubrutinib, upadacitinib, or matching placebo dose at their regularly scheduled dosing time, they should take the forgotten dose as soon as they remember as long as it is at least 10 hours before their next scheduled dose. Otherwise, they should take the next dose at the next scheduled dosing time.

Subject dosing will be recorded on a subject dosing diary. The subject will be instructed to return all drug containers (even if empty) to the study site personnel at each study visit. Study site personnel will document compliance.

Medications other than elsubrutinib, upadacitinib, or matching placebo will not be provided by AbbVie. AbbVie-provided study drug should not be substituted or alternately sourced unless otherwise directed by AbbVie.

Elsubrutinib, upadacitinib, and matching placebo will be packaged in bottles with quantities sufficient to accommodate study design. Each kit will be labeled per local requirements and this label must remain affixed to the kit. Upon receipt, study drug should be stored as specified on the label and kept in a secure location. Each kit will contain a unique kit number. This kit number is assigned to a subject via interactive response technology (IRT) and encodes the appropriate study drug to be dispensed at the subject's corresponding study visit. Site staff will complete all blank spaces on the label before dispensing to subjects. Study drug will only be used for the conduct of this study.

Table 2. Study Drug

	Investigational Product	Investigational Product	Investigational Product Placebo	Investigational Product Placebo
Investigational product name	Elsubrutinib (ABBV-105)	Upadacitinib (ABT-494)	Elsubrutinib (ABBV-105) Placebo	Upadacitinib (ABT-494) Placebo
Active ingredient	Elsubrutinib (ABBV-105)	Upadacitinib (ABT-494)	N/A	N/A
Mode/Route of Administration (ROA)	Oral	Oral	Oral	Oral

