3.12 Dispense Study Drug

Study drug will be dispensed to subjects beginning at Baseline (Day 1) and as specified in Section 2.1. The first dose of study drug will be administered after all other Baseline (Day 1) procedures are completed. At the visits specified in Section 2.1, the site personnel will review and retain a copy of the subject dosing diary, review returned study drug kits, and empty study drug packaging to verify compliance.

Elsubrutinib capsules, upadacitinib tablets, and matching placebo capsules and tablets should be dosed together at approximately the same time each day and taken with or without food.

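### SAP 6.2 counts every unit in an unreturned bottle as taken, so compliance is biased upward only and reaches 100% or more when nothing is returned or the subject is lost in the first dispensing interval

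*SAP*

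**What the plan says.** SAP 6.2 defines compliance separately for tablets and capsules. For the numerator: "The total number of tablets/capsules taken will be calculated as the total number of tablets/capsules dispensed minus the total number of tablets/capsules returned". For a missing container: "If the bottle is not returned, total number of tablets/capsules returned is assumed to be 0". The denominator is the number of days from first to last dose, both included, times the daily units: "number of tablets per day is 1 and number of capsules per day is 3". On use: "Study drug compliance will be summarized for each treatment group for SA population", with sample size, mean, standard deviation, median, minimum and maximum. The section sets no cap, no missing category and no count of subjects with unreturned bottles.

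Protocol 5.7 provides two sources of dosing information. On containers: "The subject will be instructed to return all drug containers (even if empty) to the study site personnel at each study visit". On the diary: "Subject dosing will be recorded on a subject dosing diary". Operations Manual 3.12 adds that at the scheduled visits "the site personnel will review and retain a copy of the subject dosing diary, review returned study drug kits", along with empty packaging, in order to check compliance. The SAP formula uses the containers only.

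SAP 11.2.2 lists study drug duration and compliance among the interim summaries.

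**The concern.** Not knowing what was left in a bottle is different from knowing that it was empty, and the rule treats the two alike. The denominator stops at the last dose date, so a subject who stops soon after a dispensing and keeps the bottle is credited with a full supply against a few days of treatment.

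What is at stake is the credibility of the compliance table. Data after stopping study drug are used in the efficacy analysis (SAP 8.2.1), so readers will look to exposure and compliance by arm when interpreting a weak result. If unreturned bottles are more frequent in one arm, the upward error will differ between arms, and nothing in the planned output would show it.

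**Working it through.** The documents give no compliance figure to reproduce, so the check evaluates the SAP 6.2 formula directly.

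**Inputs**
- Dispensing: Baseline and Weeks 4 to 44, every 4 weeks (Protocol Appendix D), so 12 dispensings 28 days apart.
- Doses per dispensing, B: not given. Assumed range 28 (one interval) to 35 (one interval plus the 7-day visit window).
- True adherence, a: not given. Assumed constant at 50%, 60% or 80%.
- Units per day: 1 tablet or 3 capsules. The factor 3 cancels if the three capsule bottles are handled alike, so one calculation serves both.

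**1. Direction.** An unreturned bottle from which x doses were taken contributes B instead of x. Since x cannot exceed B, the numerator rises by B − x ≥ 0. The rule never lowers the score.

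**2. Nothing returned.** The score is (number of dispensings × B) / days, and a does not appear.
- 48 weeks: 12×28/336 = 100%; 12×35/336 = 125%.
- Last dose Day 147 (five full intervals plus 7 days, six dispensings): 168/147 = 114%; 210/147 = 143%.

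**3. Lost in the first interval, bottle kept.** The score is B/d, with d the last dose day; again a does not appear.
- d = 28: 100% to 125%.
- d = 14: 200% to 250%.
- d = 7: 400% to 500%.

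**4. Only the last bottle kept, last dose on day d of interval k.** The score is [a×28(k−1) + B] / [28(k−1) + d].

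For k = 6, d = 7 (Day 147) and a = 60%: (0.60×140 + 28)/147 = 112/147 = 76%; (0.60×140 + 35)/147 = 119/147 = 81%.

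Other values with B = 28, for d = 28 and d = 7:

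| Interval of last dose | True 50% | True 80% |
|---|---|---|
| 2nd | 75% to 120% | 90% to 144% |
| 3rd | 67% to 89% | 87% to 116% |
| 6th | 58% to 67% | 83% to 95% |
| 12th | 54% to 58% | 82% to 87% |

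**5. 48-week completer, a = 60%, u of 12 bottles unreturned.** The score is [0.60×28×(12−u) + B×u] / 336.

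| u | B = 28 | B = 35 |
|---|---|---|
| 0 | 60% | 60% |
| 1 | 63% | 65% |
| 3 | 70% | 76% |
| 6 | 80% | 93% |
| 12 | 100% | 125% |

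**6. After removing the unreturned interval.** The Day 147 subject in step 4 scores (0.60×140)/140 = 60%, the assumed true value. An accurate diary for the last interval would give the same.

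**The case against.** The strongest reply is that little depends on this table. SAP 4.0 defines only the Full Analysis Set and the Safety Analysis Set. There is no per-protocol set or compliance threshold, and no efficacy analysis uses compliance. The adverse event rates per 100 patient-years in SAP 9.2.4 use exposure duration, not compliance. Other evidence also bears on non-use: plasma concentrations at several visits (Operations Manual 3.6), BTK assays (Operations Manual 3.7), and treatment duration and premature discontinuation by arm (SAP 5.0 and 6.1). Scores above 100% would show in the reported maximum. All of this stands and limits the consequence. It does not correct the number: a 60% adherer shown at 76% looks unremarkable in any maximum, and drug levels at a handful of visits say little about day-to-day intake.

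Three stronger readings are tempting and not supported.
- **The least adherent subjects score about 100%.** No section links low adherence to non-return, and a poor adherer who returns every bottle is scored correctly (step 5, u = 0).
- **Anyone who stops mid-interval and keeps the bottle exceeds 100%.** Step 4 shows otherwise for later losses.
- **Arm means are inflated by a known amount.** If 10% of an arm returned nothing, truly took 60% and had last dose on Day 147, the mean would rise by 0.10×(114% − 60%) = 5 points to 0.10×(143% − 60%) = 8 points. The 10% and the 60% appear in neither document.

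A fair objection to a diary-based remedy is that the diary is copied at visits, so a subject lost to follow-up may leave no copy for the last interval. Nor do the documents say that diary doses enter the database. Removing the interval would then leave a subject lost in the first interval with no data at all. The fix has to say what happens to that subject.

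**Conclusion.** The point holds in limited form. The stated rule scores missing returns as full intake, and the resulting bias is upward only. If each dispensing covers at least its interval, the score is 100% or more regardless of intake when no bottle is returned or the subject is lost in the first interval. With a single late bottle missing the excess is smaller: 16 to 21 points in the Day 147 example (76% to 81% against 60%), and 3 to 5 points for a completer missing one of 12 bottles. These sizes rest on the assumed 28 to 35 doses per dispensing and on constant adherence. How many subjects would be affected cannot be told from the documents.

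The consequence is a misleading descriptive table by arm, which also formed part of the interim summaries. A reader might infer that the trial's efficacy conclusions, or the reading of a null result as full exposure, depend on it. The documents do not support that, because no efficacy analysis uses compliance and other exposure evidence is collected.

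**What to change.** Replace the note in SAP 6.2 with a rule of this kind:
- For an unreturned bottle, take the doses for that dispensing interval from the dosing diary where it is available.
- Otherwise remove the interval from both numerator and denominator.
- Report a subject with no evaluable interval as having missing compliance, rather than letting the subject drop out of the table unmentioned.

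Tabulate by arm the number of subjects with at least one unreturned bottle, with missing compliance, and with compliance above 100%. Keep the present calculation as a sensitivity row labelled as an upper bound.

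The cost is SAP wording and a little programming. The removal rule needs no new data; the diary step does if diary doses are not in the database. Reported compliance will be slightly lower, and some subjects lost early will have no compliance value. The interim summaries have already been produced, so the change can apply only to the Week 24 Primary Analysis and the Final Analysis.

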7.0 Demographics, Baseline Characteristics, Medical History, and Prior/Concomitant Medications

Demographics, baseline or disease characteristics, medical history, and prior and concomitant medications will be summarized for the FAS overall and by treatment group. Categorical variables will be summarized with the number and percentage of subjects; percentages will be calculated based on the number of non-missing observations. Continuous variables will be summarized with descriptive statistics (number of non-missing observations, mean and standard deviation, median, minimum and maximum).

7.1 Demographics and Baseline Characteristics

The following demographic and baseline characteristics, as measured at baseline of the study, will be summarized.

Demographic Characteristics

- Sex (male, female)
- Age (years)
- Age category [18 – < 40 years old, 40 – < 65 years old, ≥ 65 years old]
- Ethnicity (Hispanic or Latino, Not Hispanic or Latino)
- Race (White, Black or African American, American Indian or Alaska Native, Native Hawaiian or Other Pacific Islander, Asian, Other)
- Geographic region (North America, South/Central America, Western Europe, Eastern Europe, Asia Japan, Asia Other, Other)
- Weight (kg)
- Weight Categories (< 60 kg, ≥ 60 kg)
- Height (cm)
- Body Mass Index (BMI) (kg/m²)
- BMI Category (kg/m²) (BMI < 25, BMI ≥ 25)

Other Baseline Characteristics

The following continuous variables will be summarized:

- SLEDAI-2K score
- Patient's Global Assessment of Disease Activity score
- Physician's Global Assessment of Disease Activity score
- LupusQoL score
- SF-36 score
- Time since onset of lupus (years), which will be calculated as follows:

Time since onset of lupus (years) = year of first dose – year of initial diagnosis of SLE

- Number of tender joints (from 28-tender joint count)
- Number of swollen joints (from 28-swollen joint count)
- Daily prednisone equivalent dose of corticosteroid (mg/day)
- CLASI Total Activity Score
- CLASI Total Damage Score
- Complement C3 and C4 levels
- Anti-dsDNA level
- Urine protein to urine creatinine ratio
- Serum immunoglobulin (Ig)G and IgM concentrations
- Serum creatinine

The following categorical variables will be summarized:

- Anti-dsDNA status (positive defined as ≥ 30 IU/mL)
- SLEDAI-2K status (< 10 or ≥ 10)
- British Isles Lupus Assessment Group (BILAG) organ system involvement at baseline (yes or no for each organ system domain). Involvement requires a baseline BILAG disease activity score of A or B.
- BILAG A organ system involvement at baseline (yes or no for each organ system domain).
- SLEDAI-2K organ system involvement at baseline (yes or no for each organ system domain).
- C3 status (less than the lower limit of normal [LLN]) (< 90.0 mg/dL)
- C4 status (less than LLN [< 10.0 mg/dL])
- Anti-Smith antibodies (≥ 30 AU/mL) (yes or no)
- Corticosteroid use (yes or no), and within those taking corticosteroids, ≤ 10 mg/day or > 10 mg/day.
- Corticosteroid use (yes or no), and within those taking corticosteroids, ≤ 7.5 mg/day or > 7.5 mg/day.

- Immunosuppressant use (yes or no):
 - Mycophenolate use (yes or no)
 - Azathioprine use (yes or no)
 - Methotrexate use (yes or no)
 - Tacrolimus use (yes or no)
 - Cyclosporine use (yes or no)
 - Leflunomide use (yes or no)
- Antimalarial use (yes or no):
 - Hydroxychloroquine (yes or no)
 - Chloroquine (yes or no)
 - Quinacrine (yes or no)
- Clinical Tests at Screening:
 - Chest x-ray
 - Tuberculin PPD skin test, QuantiFERON TB Gold test
 - Serum pregnancy test
- Immunization History
 - Herpes Zoster immunization
 - Hepatitis B immunization
- Tobacco/Nicotine and Alcohol Use
 - Tobacco/Nicotine Use (current, former, never, or unknown)
 - Alcohol Use (current, former, never, or unknown)

7.2 Medical History

Medical history data will be coded using the Medical Dictionary for Regulatory Activities (MedDRA). The actual version of the MedDRA coding dictionary will be noted in the statistical tables and clinical study report. Medical history data will be summarized and presented for the FAS population using body systems and conditions/diagnoses as captured on the CRF. The body systems will be presented in alphabetical order and the conditions/diagnoses will be presented in alphabetical order within each body system.

The number and percentage of subjects with a condition/diagnosis will be summarized for each treatment group as well as overall. Subjects reporting more than one condition/diagnosis within a body system will be counted only once for that body system. No statistical comparison will be performed for medical history reporting.

7.3 Prior and Concomitant Medications

Prior and concomitant medications will be summarized by each treatment group as well as overall for the FAS. Prior medications are those medications taken prior to the first dose of study drug. These include medications with a start date before the first study drug administration date, regardless of the end date of these medications. Medications taken on the day of the first dose of study drug are not counted as prior medications. Concomitant medications are those medications, other than study drug, taken after the first dose of study drug and within 1 day of the last dose of study drug. This includes medications with a start date between first study drug administration and last study drug administration + 1 day, as well as medications with a start date prior to first dose of study drug and which are ongoing after first dose of study drug. Medications taken on the day of the first dose of study drug are counted as concomitant medications.

The number and percentage of subjects who received a prior medication and the number and percentage of subjects who received a concomitant medication will be tabulated separately by the generic name assigned by the most current version of the World Health Organization (WHO) Drug Dictionary.

8.0 Efficacy Analyses

8.1 General Considerations

All efficacy analysis will be performed in the FAS.

AbbVie may terminate this study prematurely at any time, either in its entirety or partially (discontinue 1 or more treatment groups based on interim analysis), at any site. In the

event the study is partially terminated, efficacy analysis will be performed separately for the terminated treatment groups and for the continued treatment groups:

Terminated Treatment Groups

For terminated group(s), the descriptive statistics will be provided by treatment group for the following efficacy endpoints using observed case (OC) (defined in Section 8.3) through Week 48:

- Achievement of SRI-4 and steroid dose \leq 10 mg prednisone equivalent QD.
- Achievement of SRI-4.
- Achievement of BICLA.
- Number of mild, moderate, or severe flares per patient-year (respectively and overall) by SELENA SFI, assessed by number and types of flare per subject through Week 24 and Week 48.
- Steroid burden, assessed as change from Baseline.

The statistics include number of observations, mean, standard deviation, minimum, median, and maximum for continuous variables, and number and percentage of subjects for categorical variables.

Continued Treatment Groups

For continued treatment groups, the primary and secondary efficacy endpoints will be analyzed at the alpha level of 0.1 (two-sided). Multiplicity control is not planned for this study.

For all efficacy endpoints, the descriptive statistics will be provided by treatment group. The statistics include number of observations, mean, standard deviation, minimum, median, and maximum for continuous variables, and number and percentage of subjects for categorical variables.

Unless otherwise specified, any subject who is randomized based on a wrong stratum will be analyzed according to the actual stratum that the subject belongs to.

"Baseline" refers to the last non-missing observation before the first administration of study drug, or randomization if no study drug is given.

8.2 Handling of Potential Intercurrent Events

Potential intercurrent events considered in this study include 1) premature discontinuation of the study drug; 2) initiation of rescue medications; 3) initiation or dose escalation of SLE-related corticosteroid. Intercurrent events will be handled using the following methods for the efficacy analysis:

8.2.1 Premature Discontinuation of Study Drug

Data collected will be used regardless of premature discontinuation of the study drug.

8.2.2 Initiation of Rescue Medications or Initiation or Dose Escalation of SLE-Related Corticosteroid

Data collected on or after the occurrence of the rescue medications or initiation or dose escalation of SLE-related corticosteroid will be handled using the methods below for the efficacy analysis:

1. [REDACTED]
2. [REDACTED]
3. [REDACTED]

- 4. [REDACTED]
- 5. [REDACTED]
- 6. [REDACTED]

Intercurrent events above apply to all categorical endpoints. For continuous endpoints, data after intercurrent events above will be excluded from modeling (i.e., predicted from the model for analysis).

